6.2 Assessing, recording, and reporting of adverse events

For the purposes of this study, all serious adverse events (regardless of relationship) must be reported. Only nonserious adverse events that are related to the device, procedure, or the participant's ENT condition(s) should be reported. Nonserious adverse events that are not related to the device, procedure, or ENT conditions should not be reported.

An adverse event may be volunteered spontaneously by the participant or discovered by the investigator or study staff upon questioning or physical examination of the participant. The following information should be reported for all reportable adverse events and updated as needed until the event resolves:

- Adverse event (diagnosis associated with the main complaints or symptoms)
- Date the adverse event occurred
- Date the investigator (or staff) became aware of the adverse event

- Adverse event details (main complaints or symptoms)
- Relationship to study device
- Relationship to the study procedure
- Seriousness of the adverse event.
- Interventions undertaken
- Status of the adverse event (ongoing, resolved, unresolved but stable, death)
- Date of event resolution, if applicable

Source documents (eg, procedural notes, treatment notes, clinical summary) may be required as supporting documentation for an adverse event.

Any serious device- or procedure-related adverse events should be reported to the sponsor as soon as possible (preferably within 24 hours) after the investigator or clinic staff become aware of the event. Initial report of the event can be by email and/or telephone call to a sponsor representative.

During the study, **all** participant deaths must be reported to the sponsor within **24 hours** of the investigator's (or designated staff's) knowledge of the death. Deaths should be reported as the reason for study exit and the cause of the death should be reported as an adverse event. A copy of death records, medical records for the event(s) that led to the participant's death, death certificate (if available), and an autopsy report (if performed) should be deidentified and sent to the sponsor as soon as they become available for any death deemed related to the device and/or procedure.

7 Protocol Deviations

Investigators are required to adhere to the study protocol, applicable national or local laws and regulations, and any conditions required by the applicable IRB or regulatory authority.

A protocol deviation is used to describe situations in which the protocol was not followed (including all required activities at each scheduled visit or activities occurring outside of the study windows).

An investigator must notify the sponsor and the applicable IRB of any deviation from the study protocol done to protect the life or physical well-being of a participant (medical emergencies). Such notice should be given within 24 hours. The sponsor will determine if the participant affected is eligible to continue in the study.

Deviations identified by the investigational center, the monitor, or other sponsor representative(s) will be documented in the study records for tracking compliance with the protocol. The investigational centers will be required to document actions taken to prevent recurrence of deviations. The sponsor representative may initiate corrective actions based on individual deviations or trending reports, as appropriate.

8 Labeling

An additional sticker will be added to the existing FDA-cleared labeling (package labels) for the ClariFix device to indicate the device is "for study use only".

9 Administrative Information

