2.10.4 Randomization and blinding

Randomization assignments will be generated by in independent statistician using variable block size distribution by site with a 1:1 allocation to active or sham treatment. Randomization will also be stratified by allergy subgroup (allergic, nonallergic). The randomization schedule will be entered into the Medrio electronic data collection (EDC) randomization module. Randomization will occur on the day of the procedure and after all baseline data have been collected and eligibility has been confirmed. All randomized and treated participants will be considered enrolled. Confirmation of randomization assignment from EDC will be printed and filed in the study record.

This is a single-blind study; participants will be blinded to the randomized assignment. To facilitate blinding, control participants will undergo a sham procedure using the ClariFix device without a cryogen cannister. To support blinding, participants will wear blindfolds during the procedure to limit any visual clues that may suggest the treatment assignment. A separate device with a canister held near the participant will be used to provide the sound of the gas release from the cannister. A standardized script for the physician/staff will be used during the procedure to assure blinding. Additionally, local anesthesia regimes will be the same for both treatment groups within each investigational center.

Participants will complete a blinding questionnaire at completion of the procedure and at the 30-day and 90-day follow-up visits to assess the adequacy of the blinding procedures. Upon

completion of their 90-day visit, each participant will be unblinded. Sham control participants will be offered the opportunity to receive active treatment if they wish and still meet eligibility criteria.

Before the 90-day visit, unblinding of participants will only occur when medically necessary. In the event of a device-or procedure-related SAE, the sponsor may authorize the site to unblind the participant in order to adequately assess the event.

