2.10.5 Procedure (Active and Sham)

Pregnancy testing

Before the procedure, urine pregnancy tests are required for all women of childbearing potential. In the case of pregnancy, use medical judgement to select appropriate procedural anesthesia medications (eg, low doses of epinephrine and lidocaine) that are safe for use during pregnancy.

Procedure anesthesia

The local anesthesia regimen for the procedure for both active and sham treatments will be performed according to the physician's usual practice. Information regarding the anesthesia regimen will be documented in the study records.

Study procedure

Below is a high-level description of the procedure for both the active and sham procedures. Detailed instructions on the preparation, usage, and storage of the ClariFix device is available in the instructions for use (packaged with the device). To maintain the participant blind during the procedure, the sham devices will be identical to the active devices except the cryogen cannister will not be inserted into the device.

- 1) Review and update concomitant medications.
- 2) Perform quantitative endoscopic rhinoscopy before administration of nasal decongestant to evaluate nasal congestion.
- 3) Administer decongestant. If the participant is a woman of childbearing potential, use medical judgement to select a decongestant (eg, oxymetazoline) that is safe to use during pregnancy.
- 4) Perform quantitative endoscopic rhinoscopy to assess degree/extent of rhinorrhea and postdecongestant nasal congestion, and plan target treatment placement at the middle meatus.
- 5) Administer local anesthesia to both sides of the nasal cavity.
- 6) Have the participant put on the blindfold.
- 7) Prepare the ClariFix device according to the IFU (for sham treatment, do not insert the cryogen cannister).
- 8) Place the cryoprobe in firm contact with the targeted middle meatus tissue under visual guidance.

- 9) For active treatment: initiate the flow of cryogen for a total of 30 seconds and, using endoscopic visualization, ensure the cryoprobe is functioning.

 For sham treatment: turn on the device and leave the cryoprobe in contact with tissue for the 30 seconds, tissue will not freeze with the sham treatment. Use a separate device held near the participant to provide the sound of gas release from the cannister.

 For both treatments, during this time, instruct the participant breathe in and out through their mouth.

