3.2 Potential risks

Study participants will be informed of all known potential side effects and complications associated with study treatment and study assessments before consenting for the study. The risks associated with participating in the study are the same as those that the participant would have if treated with nasal cryotherapy outside of the study.

While endoscopic rhinoscopy is generally known to be safe, anticipated risks may include, but are not limited to:

- Temporary pain, discomfort or irritation
- Bleeding
- Cerebrospinal fluid (CSF) leak

Similarly, while generally known to be safe, submucosal placement of a needle and delivery of local anesthesia may be additionally associated with the following risks, not limited to:

- Minor bleeding
- Pain with injection
- Facial numbness or tingling
- Sedation
- Tachycardia, nervousness, anxiety
- Lightheadedness, dizziness, confusion
- Muscular twitching, tremors
- Infection
- Allergic reaction
- Lidocaine or tetracaine toxicity with overdose

- Visual disturbance
- Vomiting
- Headache
- Tinnitus
- Seizures
- Hypotension, bradycardia
- Unconsciousness
- Respiratory arrest
- Cardiac arrest

In addition, the specific nature of cryosurgery using the ClariFix device results in a known potential for adverse events related to the cold application, including but not limited to:

- Bleeding
- Crusting and/or tissue sloughing
- Swelling
- Pain/discomfort and/or facial pain
- Increase in nasal congestion
- Intranasal scarring/nasal obstruction
- Sensory alterations (numbness, tingling) in the face/mouth

- Headache
- Dry nose
- Ear blockage
- Septal perforation
- Vasovagal reaction
- Infection
- Dry eyes, optical changes or orbital damage

Also refer to the manufacturer's Instructions for Use (IFU) provided with the device.

There is also a possible risk of a loss of confidentiality. The sponsor will take all reasonable efforts to prevent the release of confidential participant information in accordance with the local and national privacy laws.

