6.1 Adverse events and serious adverse events

An adverse event (AE) is any undesirable clinical occurrence experienced by the participant during the follow-up period regardless of the event's relationship to either the study device or procedure. An underlying disease that was present at the time of enrollment is not an AE; however, any increase in the severity of an underlying disease is an AE.

A serious adverse event (SAE) is an event that results in any of the following:

- Death
- Life-threatening
- Hospitalization or prolongation of an existing hospitalization
- Invasive surgical intervention to correct or prevent further injury
- Persistent or significant disability or incapacity
- An important medical event

An important medical event that may not meet one of the above definitions might be considered as an SAE if it jeopardizes the health of the participant or requires surgical intervention to prevent one of the outcomes listed in the above definition.

An elective hospitalization/intervention that was planned before the participant enrolled in the study is not considered an SAE as defined above.

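### Nonserious adverse events are filtered by a relatedness judgement not stated to be blinded, so any between-arm comparison of them through day 90 is open to arm-dependent ascertainment

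*Combined protocol and SAP*

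**What the plan says.** Section 6.1 defines an adverse event broadly, as "any undesirable clinical occurrence experienced by the participant during the follow-up period", and adds that this holds "regardless of the event's relationship to either the study device or procedure". Section 6.2 then sets a narrower reporting rule for this study. For serious events there is no filter: all "serious adverse events (regardless of relationship) must be reported". For nonserious events there is one: "Only nonserious adverse events that are related to the device, procedure, or the participant's ENT condition(s) should be reported", followed by "Nonserious adverse events that are not related to the device, procedure, or ENT conditions should not be reported". Relationship to device and to procedure are data fields, but they are completed only for events that have already qualified as reportable.

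On blinding, section 2.10.4 states: "This is a single-blind study; participants will be blinded to the randomized assignment". It also has the printed assignment filed in the study record. The operator must know the arm, since the procedure steps in section 2.10.5 include the instruction "for sham treatment, do not insert the cryogen cannister". The protocol does not say who judges relatedness. It describes no blinded assessor and no independent adjudication.

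The one prespecified between-arm safety endpoint (sections 2.3.2 and 2.11.2) is the percentage of participants with a device- or procedure-related serious event through day 90.

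**The concern.** Randomization against a sham lets event rates be compared by arm without anyone deciding what caused each event. A relatedness filter applied before recording gives up part of that advantage for nonserious events, because the decision can depend on knowing the arm.

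Section 3.2 says that "the specific nature of cryosurgery using the ClariFix device results in a known potential for adverse events related to the cold application". Its list includes headache, dry eyes, optical changes and vasovagal reaction. These are not plainly ENT conditions, a term that section 6.2 leaves undefined. Section 2.9 places migraine among ENT and head-and-neck conditions for medication recording, so sites could reasonably classify headache differently. A site that judges such an event unrelated is told to leave it out.

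Nonserious events may also carry most of the safety information. The pilot in section 1.2 saw no device- or procedure-related serious events in 27 participants. Section 11 allows the outcomes through 90 days to be published separately, so event rates by arm may well be shown. The sham comparison ends at day 90, when participants are unblinded and sham participants cross over or exit. An event not recorded by then cannot be put back into the adverse event data.

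**Working it through.** The plan gives no nonserious event rate and no figure for how often events are judged related, so it has no number to reproduce on this point. The size can only be illustrated.

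**Inputs**
- From the plan: 128 participants randomized 1:1 (section 2.6), so 128 / 2 = 64 per arm.
- Assumed: true event rate p of 10%, 20% or 30%, equal in both arms.
- Assumed: probability r that an event passes the filter, 90% in the active arm and 90%, 70% or 50% in the sham arm.

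**Formula**

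Recorded rate = p × r in each arm. Apparent risk ratio = true risk ratio × (r active / r sham).

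**Equal true rates**

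| r active / r sham | Apparent risk ratio | Recorded difference at p = 10%, 20%, 30% |
|---|---|---|
| 90% / 90% | 0.90 / 0.90 = 1.00 | 0, 0, 0 points |
| 90% / 70% | 0.90 / 0.70 = 1.29 | 2, 4, 6 points |
| 90% / 50% | 0.90 / 0.50 = 1.80 | 4, 8, 12 points |

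For example, at p = 20% with 90% / 50%, the recorded rates are 0.20 × 0.90 = 18% and 0.20 × 0.50 = 10%. Across the two unequal rows, the spurious difference runs from 64 × 0.02 = 1.3 to 64 × 0.12 = 7.7 participants in an arm of 64.

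**Opposite direction**
- Swapping the probabilities gives 0.70 / 0.90 = 0.78 and 0.50 / 0.90 = 0.56.
- A real excess can also vanish. True rates of 10% active and 5% sham, with 50% and 100% reported, are recorded as 0.10 × 0.50 = 5% and 0.05 × 1.00 = 5%.

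**What this shows**

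The filter alone does not bias the ratio. With equal reporting it only lowers the counts, and shrinks any real absolute difference by the factor r. Bias in the ratio needs attribution that differs by arm. The design permits that but does not make it certain, and nothing in the documents fixes its direction.

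**The case against.** The strongest reply is that the filter is narrow and touches a comparison the plan does not make. Most of this stands.

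- **Serious events.** A reader might infer that the sham arm cannot support any unbiased safety comparison. The documents do not support that: every serious event is reported whatever its relationship, so an all-cause serious event comparison escapes this filter. The prespecified endpoint does rest on relatedness judged without a stated blind. That is a separate matter, and the complete serious event data allow a sensitivity analysis.
- **No planned test.** Sections 2.3.2, 2.7 and 2.11.2 specify no between-arm comparison of nonserious events.
- **Other routes in.** Sham participants also receive decongestant, endoscopy, local anesthesia and probe contact. Headache and visual disturbance are listed in section 3.2 as anesthesia risks, so either can be called procedure-related in the sham arm. The ENT-condition route admits events not attributed to device or procedure. A vasovagal reaction during the procedure or the observation period of at least 30 minutes has an obvious procedural link in either arm. Pain of 7 or more in that period must be reported in both arms without attribution (section 2.10.5).
- **Partial backstops.** Blinded participants complete the RQLQ(S) and EQ-5D-5L in both arms, and medications for migraine and similar conditions are recorded throughout. These soften the loss of information but cannot rebuild an adverse event table.
- **Proportionality.** The device is cleared and used on-label (section 4.1), so selective collection is a legitimate economy. Section 6.2 narrows reporting expressly for this study, so its difference from section 6.1 is not a contradiction.

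What remains is that some event types named as risks in section 3.2 can be left unrecorded on a judgement that may depend on the arm.

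**Conclusion.** The point holds as a minor design weakness. Any comparison of nonserious events by randomized arm through day 90 is vulnerable to arm-dependent ascertainment, of unknown direction and a size the documents cannot supply. Under the assumed reporting probabilities the apparent risk ratio lies between 0.56 and 1.80 when the true ratio is 1, and equals 1.00 when attribution is the same in both arms.

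This rests on two inferences from the single-blind design, the procedure steps and site reporting of events: that site staff make the relatedness judgement, and that those staff may know the arm. The protocol states neither outright. A reader might go further and infer that recorded rates will be distorted, or distorted in the device's favor. Nothing in the documents establishes either.

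**What to change.** Amend section 6.2 and the adverse event form instructions so that, through the 90-day visit of the randomized phase, at least every nonserious event of a type listed in section 3.2 is recorded in both arms whatever its judged relationship. Keep relationship to device and procedure as separate fields. Tabulate these events, and all-cause serious events, by randomized arm both with and without attribution. The present rule can stand after day 90. The change extends the attribution-free approach that section 2.10.5 already takes to severe pain in the waiting period.

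State the limit openly: the lists in section 3.2 are not exhaustive, so unlisted nonserious events would remain subject to the filter. Recording all nonserious events through day 90 would close that gap at greater cost. Having relatedness judged by someone blinded to arm would instead address the dependence on arm.

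The cost is an amendment, revised form instructions and some extra nonserious entries for 128 participants over the procedure, 30-day and 90-day visits. The sponsor's analysis of related events is unaffected. The change works only prospectively.

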9.1 Investigational center selection

The study will be conducted at up to 12 investigational centers in the US. Centers will be evaluated to ensure each center has the capacity and capability to obtain informed consent and comply with all protocol requirements. The investigators and investigational center personnel are required to comply with the principles of Good Clinical Practices (GCP) as described in the FDA regulations.

9.2 Training

The training of investigational center personnel will be the responsibility of the sponsor or sponsor-authorized representatives. All treating physicians must be proficient in the use of endoscopic techniques. All physicians will be trained on the preparation and use of the ClariFix device before participant enrollment in this study.

To ensure uniform data collection and protocol compliance, the sponsor or sponsor-authorized representatives will review all components of the study with the study coordinator(s)/study staff at each investigational center. The review will include the study protocol, techniques for the identification of eligible patients, instructions for data collection during the procedure, schedules for follow-up, and training on the EDC system.

9.3 Informed consent process

Informed consent must be obtained in accordance with US regulation 21 CFR 50. The participants must be informed about their right to withdraw from the study at any time and for any reason without sanction, penalty, or loss of benefits to which the participant is otherwise entitled and also informed that withdrawal from the study will not jeopardize their future medical care. The standard institutional patient consent form does not replace the study informed consent form (ICF).

The sponsor will provide a study-specific ICF template to the central IRB and to each investigational center under jurisdiction of a local IRB. For sites under the jurisdiction of a local IRB, the template may be modified to suit the requirements of the individual investigational center; however, the sponsor must preapprove all changes to the ICF before initial submission to the IRB. The IRB-approved consent form must be sent to and approved by the sponsor before the first device shipment. All investigational centers must retain one copy of the IRB-approved ICF in the study files along with the other investigational forms.

Each enrolled participant must be given a copy of their signed consent form and the original

must be retained in the investigational center study file for that participant. A copy may also be sent to medical records, if required by institutional policy. Informed consent documents must be available for review by the sponsor during monitoring visits.

Modifications to the study-specific ICF and/or any other written information distributed to participants must be preapproved by the sponsor and the IRB, as necessary.

9.4 Confidentiality

All information and data sent to the sponsor concerning participants or their participation in this study will be considered confidential. Participants will be identified by a study-specific identification code. All data used in the analysis and reporting of this investigation will use the study-specific codes and will not include identifiable references to individual participants. Any source documentation must be deidentified by the investigational center before being sent to the sponsor.

The investigator will allow visits by the sponsor representatives and the US FDA inspectors or any other local governmental body to review the study participants' medical records.

9.5 Institutional Review Board (IRB)

It is the investigator's responsibility to obtain and maintain written approval of the final investigational plan and ICF from the applicable IRB. The investigator is responsible for submitting and obtaining initial and continuing review of the study by the IRB. It is also the investigator's responsibility to notify the IRB of any amendments to these documents. Written IRB approval must identify the study by title and version, document the date of review, and be forwarded to the sponsor before the first device shipment.

The investigator must keep all study-related correspondence with the IRB on file and forward copies of such correspondence to the sponsor.

It is anticipated that the central IRB listed below will be used for most, if not all, investigational sites. The sponsor may help facilitate submissions to the central IRB on behalf of the investigators.

Advarra IRB [name]

